the participant remains in the study for purposes of data collection for outcomes only a separate “Age of Majority” informed consent will be obtained.

O. PROCEDURES TO BE EMPLOYED IN ANALYZING DATA AND THE ANTICIPATED SIGNIFICANCE OF THE PROPOSED STUDY

Analyses will be conducted with SPSS and SAS software programs. Probability levels of < .05 will be used as cut offs for statistical significance.

The key significance of this study is the identification of a reduction in inflammatory cytokines, and increase in hfHRV. With this study, we hope to lay the foundation for the application of AED for pediatric functional GI disorders by demonstrating improvement in mitochondrial bioenergetics and reduction in inflammation as part of the pathophysiology. This is an innovative and novel understanding of the pathophysiology of FGID, which will enhance our knowledge on the brain-gut neural connectivity underlying functional disorders and ultimately improve patient care.

P. FINANCIAL RELATIONSHIPS

The EAD devices will be supplied by the distributing company (IHS) at manufacturing rate. A grant from Advancing a Healthier Wisconsin (AHW) will partially support this proposal and a CTIS Start Up Pilot award (\$12000) funding decision is pending. Patients will receive a stipend of \$20 at each of the following visits: Visit 1, Visit 4 and Visit 5. (After each blood draw is completed)

Q. ADVERTISEMENTS / FLIERS

Not applicable.

R. BIBLIOGRAPHY

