- Subjects will meet Rome IV criteria for functional nausea, irritable bowel syndrome, dyspepsia or functional abdominal pain as determined by a pediatric gastroenterologist
- Patients must have an intact external ear that is free of infection or severe dermatological conditions, have stable vital signs for their respective age, no history of seizures and no currently implanted electrical device

Exclusion Criteria:

- Mental retardation or pervasive developmental disorder or epilepsy
- Psychosis
- Genetic or chromosomal disorders
- Pregnancy
- Subjects who admit to substance abuse during screening
- Patients with findings of peptic ulcer disease, H.pylori gastritis, celiac disease, inflammatory bowel disease, allergic disorders, or any chronic condition or medication that may cause nausea or pain
- Patients who are treated with opioids or who had any changes in their medical regimen in the past four weeks prior to study
- Patients with a history of allergy to adhesives

Study Design Overview

Subjects will undergo medical workup per standard of care. Subjects refractory to current medical therapy may be enrolled without changes to their current medical treatment. No new pharmacological agents will be added during the 4-week study period and no changes in dosing or scheduling of current therapy will be allowed during the study period. Subjects will be screened weekly for any side effects by registered nurses who are part of the Pediatric Translational Research Unit (pTRU). All subjects will be asked to notify the PI or research team with any worsening in symptoms or side effects of therapy. If symptoms worsen or fail to improve during the study or if their clinical presentation changes in any way, subjects will have the option to drop out any time, receive standard medical therapy and appropriate referrals. If per standard of care, a subject requires a change in one or several of their regular medications during the study, they will be asked to notify the research team. To monitor this, the subjects will be inquired about their medication list and doses during their weekly visits. If the medication change is determined to potentially affect the study results, the subject may be excluded from further study as determined by the PI.

Protocol and Procedures

Pre (Baseline):

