The primary investigator, a co-investigator or research coordinator will introduce the study to eligible patients seen in the CHW Autonomic and Gastroenterology Clinic during their regularly scheduled clinic visit or while

admitted to the hospital (at the end of admit). A member of the research team will explain the details and purpose of the study during an informed consent discussion. Once the patient and caregivers have had enough time to consider participation, understand all of the risks and benefits and would like to participate, they will complete the informed consent, assent and HIPAA documents.

Medical and psychological history will be obtained to verify eligibility and screen patients for alcohol, nicotine, and drug abuse following the completion of consent/assent documents. All eligible subjects will complete the questionnaires related to demographic and the Functional Disability Inventory (FDI). This will take about 5-10 minutes total to complete.

Visit 1 and 4: Subjects will undergo blood drawn for mitochondrial bioenergetics and have EAD placed. HRV will be measured before EAD placement at visit 1 and after EAD placement at visit 4. This visit will take about 60 min. They will complete the FDI again

Visit 2; 3: EAD will be changed and a new one will be placed.

Visit 5: This visit is about 2-3 month after the last EAD has been removed. At this visit they will undergo again blood drawn for mitochondrial bioenergetics, measurement of HRV and complete FDI.

The samples will be processed and stored in the laboratory of study research team members, [name] in Health Research Center, H5720.

E. TOTAL NUMBER OF HUMAN RESEARCH PARTICIPANTS PROPOSED FOR THIS STUDY AT THIS SITE AND GLOBALLY. WHAT ARE THESE NUMBERS BASED ON?

7 patients aged 12-18 years, who are being evaluated in the Gastroenterology or FGID clinic are eligible to participate in the FGID group.

F. DRUGS OR PROCEDURES

Table 1.

	Pre	Visit 1	Visit 2	Visit 3	Visit 4	Visit 5
Screening & Consent	x					
Heart Rate Variability		x			x	x
FDI	x				x	x
EAD		x	x	x	x	
Mitochondrial bioenergetics		x			x	x

All procedures will be performed in the Children's Hospital of Wisconsin (CHW) Pediatric Translational Research Unit (pTRU).

Measurements and Data Collection

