- g. Syncope (fainting) - Rare (event rate 1% - < 5%)

Adverse effects to supporting personnel

- a. Skin piercing with percutaneous needles - Rare (event rate 1 % - < 5%)

**In our recently completed randomized trial of auricular neuro-stimulation for functional abdominal pain there were no significant or serious adverse events noted. Of 115 enrolled subjects, 10 reported side effects for following reasons, none of which were serious: ear discomfort n=6 (three active/three placebo device); adhesive allergy n=3 (one active/two placebo); syncope due to needle phobia n=1 (placebo).

Safety Monitoring Plan

All procedures will be performed by trained professionals within the standard of care under continuous medical supervision in the hospital setting (research unit). Side effects will be inquired about and documented every week during the study and at the post-study follow-up visit. If any serious harm or discomfort is identified by the subjects or the study personnel, the treatment will be discontinued. Any patient with worsening in symptoms

during the study will be able to drop out at any time and receive standard of care medical therapy. The skin of the external ear will be carefully disinfected to avoid any infection risks. Subjects will undergo vital sign screening before enrollment and vital sign assessment before EAD placement.

Safety Analysis Plan

There are no dangerous interventions related to this study, and the short study timeline allows for discontinuation of treatment when it is proven to be ineffective.

I. PROVISION FOR THE PROTECTION OF PRIVACY OF SUBJECTS AND TO MAINTAIN THE CONFIDENTIALITY OF DATA

All research projects that collect electronic data must use appropriate security measures to ensure that data is protected from theft or loss in order to prevent breaches of confidentiality. You must indicate what encryption tools (or why they are not necessary) from the options below. The IRB will not review this protocol unless you indicate the encryption tools being used to secure your research data. If you do not have encryption in place on your systems, please contact your Information Systems support to arrange for one of the encryptions options listed below.

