Missing Data: Every effort will be made to avoid missing data. Using logistic regression, the pattern of missing data will be explored. Assuming the data are missing at random (MAR) multiple imputations for items will be used. Data analysis overview: Summary statistics, such as mean, median, standard deviation, range and correlation will be used as a first step to examine data. To satisfy parametric assumptions, we may perform transformations with justifications if possible and otherwise use non-parametric tests. We will use CART and biological and physiological information to identify interactions when formulating regression models. Statistical software employed for data analysis will be: Cytel StatXact, SAS version 9.4, Salford System CART for trees, SPSS Version 24. The power calculation was made using PASS 13.

Power

This is not applicable due to this being an exploratory pilot study. This study will be supported by a \$12000 from CTSI (if approved), and number of subject was based on budget.

We will similarly analyze the change in vagal tone at visit 1, visit 4 and visit 5 and the different variables of mitochondrial bioenergetics including basal respiration, ATP production, maximal respiration, spare respiratory capacity and extracellular respiration.

We will also compare cytokines at visit 1; 4 and 5 and if possible correlate the change in cytokines to changes in hfHRV and RMSSD.

J. PROVISIONS FOR MONITORING DATA TO ENSURE THE SAFETY OF SUBJECTS; AND ADDITIONAL SAFEGUARDS TO PROTECT THE RIGHTS AND WELFARE OF SUBJECTS WHO ARE LIKELY TO BE VULNERABLE

The PI will monitor the health of all patients in the study per standard clinical practice. The PI will monitor protocol adherence and supervise data collection, entry, and analysis.

K. ANTICIPATED BENEFITS ASSOCIATED WITH THE PROTOCOL TO HUMAN RESEARCH PARTICIPANTS AND SOCIETY

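### Subjects who do not improve may leave, but no post-baseline outcome is scheduled before Visit 4 and stoppers are not asked back, so the pre-post change may be overstated

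*Combined protocol and SAP*

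**What the plan says.** **Leaving.** Section D, Study Design Overview: "If symptoms worsen or fail to improve during the study or if their clinical presentation changes in any way, subjects will have the option" to leave and receive standard care. The same paragraph covers a medication change that might affect the results: "the subject may be excluded from further study as determined by the PI".

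**Outcome schedule.** Table 1 (section F) places HRV and mitochondrial bioenergetics at Visits 1, 4 and 5. Cytokine blood follows the same visits. FDI is taken at baseline (Pre in Table 1, Visit 1 in the text) and at Visits 4 and 5. On HRV, Protocol and Procedures says: "HRV will be measured before EAD placement at visit 1 and after EAD placement at visit 4". For the visits between: "Visit 2; 3: EAD will be changed and a new one will be placed".

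**Other weekly data.** Under Measurements and Data Collection, each device placement also records medications and doses, side effects and whether the device was worn for the full five days. None of these is an efficacy outcome.

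**Missing data.** The plan commits to trying to avoid missing data. It then says: "Using logistic regression, the pattern of missing data will be explored", and "Assuming the data are missing at random (MAR) multiple imputations for items will be used".

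**Not found.** There is no assessment at early stopping, no request for the reason for leaving, and no statement that a subject who stops the device, or is excluded, is asked to attend Visits 4 and 5.

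**The concern.** The study has one arm of 7 subjects, and its result is a change from baseline judged at p < .05 (section O). The protocol names failure to improve as an occasion for leaving. Medication is frozen during the four weeks, so a subject who is not improving and wants other treatment must either withdraw or make a change that can lead to exclusion.

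Someone who goes by either route before Visit 4 and does not return has baseline outcomes and nothing after them. If those who go are the non-responders, and symptoms move with the laboratory and HRV outcomes, the remaining subjects will show a larger change than the enrolled group had. There is no comparator arm in which the distortion could be seen. One lost subject is 1/7 = 14% of the sample, and the missing values cannot be collected later.

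**Working it through.** The plan gives no power calculation, effect size or dropout rate, so there is no figure of its own to reproduce. Everything below is illustrative.

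**Inputs from the documents**
- N = 7 (section D).
- Supine RMSSD in clinic patients whose FDI improved: 33.14 (SD 11.06) ms, then 59.11 (SD 25.04) ms (section C). Change: 59.11 − 33.14 = 25.97 ms.
- RMSSD fell in those who did not improve; the amount is not given. The comparison was 7 against 5 patients, p = 0.09, without the device. The text says 13 subjects, but 7 + 5 = 12.
- Earlier device trial: 115 enrolled (section H), 104 analysed (section K). The reasons for the difference are not stated.

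**Assumptions**
- 4 responders at +25.97 ms and 3 non-responders at 0.
- Leaving rate of either 11/115 = 9.6% or 20%.

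**1. Effect on the estimate**

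| Who leaves before Visit 4 | Completer mean (ms) | Against all 7 |
|---|---|---|
| Nobody | 4 × 25.97/7 = 14.84 | – |
| One non-responder | 4 × 25.97/6 = 17.31 | +2.47 (+17%) |
| One, non-responder with probability 0.75 | 0.75 × 17.31 + 0.25 × 12.985 = 16.23 | +9% |
| One at random | 3/7 × 17.31 + 4/7 × 12.985 = 14.84 | 0 |
| One responder | 3 × 25.97/6 = 12.985 | −12.5% |
| Two non-responders | 4 × 25.97/5 = 20.78 | +40% |
| Three non-responders | 25.97 | +75% |

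The last two rows are worst cases. Other assumptions give other sizes. If 6 subjects change by +25.97 ms and the single non-responder, who leaves, changes by 0 to −10 ms, the overstatement is 3.71 to 5.14 ms.

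**2. How often anyone leaves** (binomial, n = 7)
- At 9.6%: at least one 51%, two or more 14%, three or more 2%.
- At 20%: 79%, 42%, 15%.

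**3. Scale against sampling error.** The SD of change is √(11.06² + 25.04² − 2r × 11.06 × 25.04). With the pre-post correlation r assumed between 0 and 0.7, this is 27.4 to 19.0 ms. Dividing by √7 gives a standard error of 10.3 to 7.2 ms. The 2.47 ms shift is therefore 0.24 to 0.34 of a standard error.

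**4. False positives.** This was simulated with 7 subjects, zero true change, bivariate normal symptom and outcome changes, the worst subjects on symptoms always the ones to leave, and a paired t test at two-sided .05. The chance of a significant improvement is 2.5% when symptoms and outcome are unrelated. Weighted over 0 to 3 leavers:

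| Symptom–outcome correlation | 9.6% leaving | 20% leaving |
|---|---|---|
| 0.3 | 3.1% | 3.6% |
| 0.5 | 3.7% | 4.8% |
| 0.7 | 4.7% | 6.7% |

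**5. Can the planned imputation repair it?** In a separate simulation, subjects with below-average symptom change left with probability 0.5, and the symptom–outcome correlation was 0.6. Completer bias was 0.158 SD. Regression imputation from a baseline covariate left 0.155 SD. With correlation 0, bias was close to zero either way. The weekly medication, side-effect and wear records could be added to such a model for anyone who reached Visit 2 or 3. They are not measures of response, and 6 or fewer completers cannot support a useful model of how they relate to it.

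**The case against.** **Withdrawal must be free.** These are minors in research classed as greater than minimal risk, and the option to leave is proper. This stands. The point concerns what is collected afterwards, not the right to go.

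**Exclusion after a drug change is defensible.** It is discretionary, limited to changes that could affect results, and reasonable for a mechanistic study, since values taken under new therapy are confounded. This stands in part. It is a reason to label such values, not to leave them uncollected.

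**The plan already does something.** It promises effort against missing data, pays stipends at Visits 4 and 5, lists discontinuation by families among the study-level stopping points (section L), and gathers weekly data. All true, and it would be wrong to say that a leaver has baseline variables only. But none of this asks a stopper to return or yields an outcome. The missingness regression is described as exploratory, so its lack of power as a formal test is not held against it.

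**RMSSD is not the main aim.** The specific aim is mitochondrial bioenergetics and inflammation; RMSSD is primary only among the HRV measures. For the aim's own endpoints, a link to symptoms is assumed. This stands and limits the weight of the illustration.

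**A stronger reading to avoid.** A reader might infer from the Safety Analysis Plan, where "the short study timeline allows for discontinuation of treatment when it is proven to be ineffective", that the protocol stops individual non-responders by rule. That sentence is a general remark about the timeline and sets no subject-level criterion. A reader might also infer that the result will be biased upwards. The documents do not show that non-responders will leave, that leavers will stay away from later visits, or that symptoms track the outcomes under this device.

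**Conclusion.** The gap is real and its consequence conditional. Following the plan as written can lose the post-baseline outcomes of subjects who leave because they did not improve, and the stated missing-data methods cannot restore them with 7 subjects. Overstatement needs two things: leaving related to non-response, and symptoms related to the outcome. For RMSSD, the second rests on a small clinic comparison without the device (p = 0.09). For the mitochondrial and cytokine outcomes it is an assumption.

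The size cannot be derived from the documents. The illustrative shift of 2.47 ms for one non-responder lost is about a quarter to a third of a standard error, and the rise in false positives is modest. The main effect is on the estimate. No stated figure is shown to be wrong, and the documents do not support a claim that the trial's result is invalid. This is an inexpensive improvement of minor priority for an exploratory pilot whose size was set by budget.

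**What to change.** 1. In Study Design Overview, state that stopping the device or changing medication does not end follow-up. Invite these subjects, including those the PI takes off treatment, to the planned Visits 4 and 5. Attendance stays voluntary, and the reason for stopping is recorded.
2. Only if a subject will not continue to Visit 4, offer the Visit 4 FDI, HRV and blood draw at stopping, before new therapy starts, as a substitute.
3. Report all 7 enrolled subjects. Label values taken after early stopping, off device or after new therapy. Visit 4 HRV follows device placement, so off-device HRV should not be pooled with it without a sensitivity analysis. Visit 5 HRV is off device for everyone and can be compared directly, apart from any new therapy.
4. Show completers-only results beside results that assign no change from baseline to subjects without follow-up.

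**Cost.** Visits 4 and 5, their assays and the $20 stipends are already planned for all 7, and the early assessment replaces Visit 4, so no assays are added. Subjects remove devices at home, so an occasional unscheduled visit with a draw of about 50 ml may be needed, and some will decline. Some values will reflect less treatment or be confounded by new therapy, which is why they are labelled and the results shown side by side.

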At the time of each EAD placement, a member of the research team will inquire and document current medications and doses and if subjects experienced any side effects from the EAD during the previous week. Subjects will also be asked if they wore the device for all five days and it will be documented if the device was returned to the research team.

Demographic Information

Data will be collected as part of the clinic visit and at enrollment. This includes child's date of birth, age, sex, ethnicity, and caretaker marital status. The physician assessment will also include questions about prior medical diagnoses, co-morbid symptoms and the characteristics of pain and nausea such as timing and triggers. The FDI will be performed at visit 1; 4 and 5. This instrument has demonstrated reliability and validity and have been used for both clinical and research purposes in pediatric populations.

Medical Information

Information recorded for patients is part of clinical care and includes weight, height, vital signs, medications, gastrointestinal symptoms, early life events, family history, surgeries and other medical co-morbidities.

[figure not shown]
Heart Rate Variability

HRV reflects the variability of the R-R interval in the electrocardiogram and its frequency domains (30). HRV is an indirect measure of central autonomic control and an indicator of overall psychological well-being (31). Reductions in resting HRV reflect decreases in vagal output. The high frequency range of HRV is considered representative of vagal (parasympathetic) activity and studies show altered vagal tone as measured by HRV in subjects experiencing nausea (32). All subjects will undergo a 10 minute baseline HRV measurement (five minutes supine and 5 standing) after 10 minutes of rest. Recordings will be performed supine and standing to assess baroreflex response. HRV indices such as high and low frequency domains, low/high frequency ratio and the time domain RMSSD as a surrogate of vagal tone (30) will be analyzed using Kubios software. The RMSSD values will be the primary HRV outcome and compared to baseline (pre-EAD stimulation), post-stimulation and 2-3 month later at follow up.

We will use the following HRV collection methods; *eMotion* Faros ECG Mobile 360 and the Actiwave by CamNTech. The *eMotion* Faros will primarily used, and in the event that the faros devices are not available, the Actiwave will be available as a backup device.

eMotion Faros ECG Mobile 360

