The *eMotion* Faros ECG Mobile 360 is a remote electrocardiography monitoring system that is used for real-time HRV measurements. The ECG data will be transmitted from 3-5 electrodes (stickers) placed on the body (pictured below) to a mobile device through Bluetooth. The data can be retrieved in two ways: through a web browser for analyzing or with real time monitoring view on a computer. A password protected laptop will be used to import the data and then to import it into an HRV analysis software.

Actiwave by CamNTech

The Actiwave by CamNTech may be used to measure ECG. This device is a single channel recorder, where two electrodes (stickers) are placed on the patient's chest. A password protected laptop will be used to import the data and then to import it into an HRV analysis software.

Measurement of cytokines and mitochondrial bioenergetics: blood will be collected at visit 1; 4 and 5 and saved to perform cytokines (about 50ml). [name] Clinical Immunodiagnostic and Research Laboratory MFRC 5072, will be looking at "inflammatory markers". Which means the blood will be tested to detect increase in protein which can be an indicator for inflammation.

Neuro-stimulator

Electro Auricular Device (EAD), (EAD) treatment protocol

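### The single pre-treatment RMSSD is taken on the day of the first blood draw and first ear-needle placement, and the order of HRV and blood draw is not fixed at any visit.

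*Combined protocol and SAP*

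**What the plan says.** Section D (Protocol and Procedures) covers Visits 1 and 4 together: "Subjects will undergo blood drawn for mitochondrial bioenergetics and have EAD placed. HRV will be measured before EAD placement at visit 1". In full, the second of these sentences is "HRV will be measured before EAD placement at visit 1 and after EAD placement at visit 4". For Visit 5, two to three months after the last device comes off, it says "At this visit they will undergo again blood drawn for mitochondrial bioenergetics, measurement of HRV and complete FDI"; no device is placed then.

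The Pre visit is limited to consent, history and questionnaires: "All eligible subjects will complete the questionnaires related to demographic and the Functional Disability Inventory (FDI"). Table 1 in Section F agrees. It marks HRV at Visits 1, 4 and 5 only, and bioenergetics at the same three visits.

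The Heart Rate Variability section makes RMSSD the main HRV outcome, compares it across baseline, post-stimulation and follow-up, and asks for 10 minutes of rest followed by 5 minutes supine and 5 standing. It also says "HRV is an indirect measure of central autonomic control and an indicator of overall psychological well-being". The section on cytokines and bioenergetics says "blood will be collected at visit 1; 4 and 5 and saved to perform cytokines (about 50ml").

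Section D enrols 7 adolescents and describes no sham or untreated arm.

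**The concern.** A before-after study without a control depends on its baseline being measured under the same conditions as the later readings. Here the conditions differ. At Visit 1 the subject is about to have needles placed in the ear for the first time and has the first trial blood draw that day. At Visit 4 the procedure is familiar, but a new device has just been placed. At Visit 5 there is a draw and no placement.

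The protocol itself makes the mechanism plausible. It links HRV to psychological state, and Section K reports frequent anxiety in the team's functional nausea patients, a group eligible here. The safety data from the earlier trial include "syncope due to needle phobia n=1 (placebo"), one case among 115 enrolled.

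HRV is not incidental. The hypothesis runs from the device through vagal tone to mitochondria. Section I plans to correlate change in cytokines with change in hfHRV and RMSSD, and Section O counts a rise in hfHRV as part of the study's key significance. An error in the Visit 1 recording enters all of these contrasts.

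**Working it through.** **1. Conditions of each HRV reading** (Section D and Table 1)

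| Visit | HRV | Blood draw | Device placement | HRV relative to placement | HRV relative to draw |
|---|---|---|---|---|---|
| Pre | no | no | no | – | – |
| 1 | yes | yes, first | yes, first | before | not stated |
| 4 | yes | yes | yes, fourth | after | not stated |
| 5 | yes | yes | no | – | not stated |

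The only clues to the order of draw and HRV point opposite ways. The text for Visits 1 and 4 and for Visit 5 mentions the draw first; Table 1 lists HRV above bioenergetics. Neither is an instruction on sequence.

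**2. What this does to the contrasts**

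Write b1, b4 and b5 for the procedure-related shift in RMSSD at each visit.

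- Observed change, Visit 1 to 4 = device effect + (b4 − b1).
- Observed change, Visit 1 to 5 = persisting effect + (b5 − b1).

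If the draw has the same position at every visit, its direct effect is largely common to all readings and mostly cancels. If staff vary the order, it does not cancel. First-time anticipation sits in b1 only. For Visit 1 to 4, b4 also contains the response to a placement just made: procedural stress could lower RMSSD and acute stimulation could raise it, so the sign of b4 − b1 cannot be determined. For Visit 1 to 5 there is no placement at the later visit, so loss of anticipation is the main difference in procedure.

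**3. How much a shift could matter**

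The plan has no figure to reproduce: Section I gives budget as the basis for 7 subjects and calls power not applicable. The following is a sensitivity check only.

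Inputs:
- n = 7 (Section D).
- Significance at 0.05 (Section O); two-sided and a paired t-test are assumed.
- Supine RMSSD 33.14 ± 11.06 ms and 59.11 ± 25.04 ms at the two visits of the improved subgroup (Section C). The documents do not say whether ± is an SD or an SE.
- Within-subject correlation ρ assumed 0 to 0.9; size of shift assumed.

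Formulas and results:
- SD of change = √(s1² + s2² − 2ρ·s1·s2).
- ρ = 0: √(11.06² + 25.04²) = √749.3 = 27.4 ms.
- ρ = 0.9: √(749.3 − 498.5) = √250.8 = 15.8 ms.
- A mean change is significant when it exceeds 0.925 SD of change (t critical value on 6 df divided by √7). That is 25.3 ms at ρ = 0 and 14.6 ms at ρ = 0.9.
- The chance that a pure shift is declared significant comes from the noncentral t with parameter shift × √7 / SD of change.

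| Reading of ± | SD of change, ρ = 0 to 0.9 | 5 ms shift | 10 ms shift | 15 ms shift |
|---|---|---|---|---|
| SD, as reported | 27.4 to 15.8 ms | 7% to 11% | 13% to 29% | 23% to 56% |
| SD of 11.06 at both visits | 15.6 to 4.9 ms | 11% to 61% | 30% to 99% | 57% to 100% |
| SE (SD = SE × √7) | 72.4 to 41.9 ms | 5% to 6% | 6% to 8% | 8% to 13% |

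The nominal rate is 5%. In every row the estimated mean change is wrong by the full shift, whether or not it reaches significance.

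**4. Rest period and blood volume**

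If the draw comes first and rest follows it, the standing recording begins at least 10 + 5 = 15 minutes after the draw. The 50 ml is not stated to be per visit; reading it so is an assumption (3 × 50 = 150 ml in total), and nothing above depends on it.

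**The case against.** The case against is substantial. This is an exploratory pilot whose aim is bioenergetics and inflammation, and its root limitation is the lack of a control; habituation is one unquantified example. The rest period gives arousal time to settle. The draw recurs at all three HRV visits, so only its novelty differs. All of that stands and limits the weight of the point. It does not explain why the order should be left open, or why Visit 4 HRV should follow a placement when Visit 1 HRV precedes one.

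A reader might go further and infer that RMSSD will rise as subjects get used to the procedures. The documents do not support that. They give neither size nor sign, and Section C reports that supine RMSSD fell between visits in subjects who did not improve. That fall does not refute the concern either, since no first needle procedure is described there.

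A reader might also infer that the standing test directly follows a large draw. The order is unspecified, and rest plus the supine phase would intervene.

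Finally, a reader might expect a second baseline, averaged in, to cure the problem. Averaging reduces random error, but if Visit 1 is shifted by b1 and Pre is not, the mean still carries b1/2. Pre may also differ in setting, because it takes place at a clinic visit or at the end of an admission.

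**Conclusion.** The concern holds in a limited form. There is one pre-treatment RMSSD, taken on the day of the first draw and first placement. The order of draw and HRV is unspecified at Visits 1, 4 and 5, and no control arm or repeat baseline can show how far RMSSD moves without treatment. Procedure-related arousal may bias the change. Its size is unknown, its sign is undetermined for Visit 1 to 4, and Visit 1 to 5 is the clearer case.

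The percentages above illustrate consequences under assumed shifts, correlations and readings of ±; they do not estimate the bias in this trial. The point does not invalidate the pilot. It is worth acting on because matching the conditions costs almost nothing.

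**What to change.** In Section D, state one sequence for Visits 1, 4 and 5: 10 minutes of rest; supine then standing HRV, before any needle procedure that day; blood draw; device placement where scheduled. Add the same order as a note to Table 1. Reconcile it with the present wording that puts Visit 4 HRV after placement. If a recording after placement is also wanted, name it as a separate measurement and keep it out of the comparison with Visit 1.

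In the analysis section, state that a single uncontrolled baseline cannot separate habituation from a device effect, and that changes in RMSSD and hfHRV will be reported with that limit.

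The cost is wording and a minor change in visit flow, with no added procedure.

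Optionally, record HRV at Pre by the same method: about 20 minutes each (10 rest + 5 + 5) for 7 subjects. Report the Pre-to-Visit-1 difference descriptively as untreated variation, note any difference in setting, and do not rely on averaging the two values to remove bias.
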